5.2 Primary, secondary and exploratory endpoints

Primary endpoints for primary objectives A1 and A2:

- Maternal primary endpoint 1: Occurrence of solicited local reactions within 7 days following administration of investigational product (pain at the injection site, redness, and swelling).
- Maternal primary endpoint 2: Occurrence of solicited systemic events within 7 days following administration of investigational product (fever, nausea/vomiting, diarrhoea, headache, fatigue/tiredness, muscle pain, and joint pain).
- Maternal primary endpoint 3: Occurrence of solicited and unsolicited adverse events through 1 month after administration of investigational product.
- Maternal primary endpoint 4: Occurrence of SAEs, MAEs, and obstetric complications (peripartum, intrapartum, and postpartum) throughout the study (Visit 1 through the 12month post-delivery study visit) and any unsolicited events leading to study withdrawal.
- Infant primary endpoint 1: Occurrence of unsolicited adverse events from birth to 6 weeks of age

A placebo controlled clinical trial investigating the safety and immunogenicity of GBS6 in pregnant women with and without human immunodeficiency virus (HIV) infection and their infants

Protocol Version 5.0, Dated 01/02/2023

Protocol Version/date 5.0,01/02/2023
R&D Protocol Code Number:
Page:28

- Infant primary endpoint 2: Occurrence of SAEs, AEs of special interest (major congenital anomalies, developmental delay, and suspected or confirmed GBS infection), and MAEs through 12 months of age and any unsolicited events leading to study withdrawal.

Secondary endpoints for secondary objectives B1, B2, B3:

- Maternal secondary endpoint 1: GBS serotype- specific IgG antibody titres measured at baseline, 2 weeks, 1 month after vaccination, at delivery and 6 weeks after delivery in HIV positive and HIV negative women.
- Maternal secondary endpoint 2: GBS serotype specific IgG titres measured at baseline, and at delivery in HIV positive and HIV negative women.
- Infant secondary endpoint 1: GBS serotype specific IgG antibody titres in HIV-exposed and unexposed infant participants measured at birth, 18 weeks and 12 months of life.
- Infant secondary endpoint 2: GBS serotype specific IgG titres in HIV-exposed and unexposed infant participants measured at 18 weeks of life.
- Infant secondary endpoint 3: Placental transfer ratio of GBS-specific antibodies in HIV-exposed and unexposed pregnancies.

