6.1 Sample size

This is a Phase 2 randomised, placebo controlled, double-blinded study to assess safety, tolerability, and immunogenicity of GBS6 in pregnant HIV positive and HIV negative women and their infant participants. It will be the first evaluation of the investigational GBS6 vaccine in HIV-infected pregnant women. This study will enroll pregnant women with and without HIV to receive the GBS6 in order to provide an expanded safety and immunogenicity data set (for both pregnant women and their infants) and to support progression of the development of this vaccine. As such, the statistical analyses are largely descriptive and the sample size is chosen based on what is achievable at the site. Additionally, and consistent with the clinical phase of the study (II), the primary outcome is based on safety.

Regarding safety, for common pregnancy outcomes such as prematurity, this sample size of 300 in total would provide 80% power (5% alpha) to detect an increase in prematurity outcomes from a background rate of 10% in the placebo arm, to at least 22% in the vaccine arm.

For the secondary objectives of immunogenicity, approximately 300 pregnant women will be enrolled in this study, 150 participants at the selected GBS6 dose/formulation (75 HIV positive and 75 HIV negative) and 150 participants in the placebo group (75 HIV positive and 75 HIV negative). Based on data from a recent study (20), the standard deviation (SD) of the GMT responses to serotypes Ia, Ib and III is expected to be around 2.55 log e units.

With 75 women per group, the study will have at least 80% power (5% alpha) to detect at least 3.24-fold higher antibody responses post-vaccination in vaccinated participants compared with placebo.

A placebo controlled clinical trial investigating the safety and immunogenicity of GBS6 in pregnant women with and without human immunodeficiency virus (HIV) infection and their infants

Protocol Version 5.0, Dated 01/02/2023

Protocol Version/date 5.0,01/02/2023
R&D Protocol Code Number:
Page:31

	HIV-uninfected pregnant women	HIV-infected pregnant women
Placebo	Group 1 (n=75)	Group 3 (n=75)
GBS6 vaccine	Group 2 (n=75)	Group 4 (n=75)

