- Maternal exploratory endpoint 3: For each serotype, IgA/IgG GMCs will be calculated at all breast milk visits for each group with 95% confidence intervals. Groups 1 vs 2, 3 v 4 will be compared using similar methods to those for blood IgG concentrations.

- Infant exploratory endpoint 1: The proportion of infant participants achieving defined levels of IgG to diphtheria toxoid and 13-valent pneumococcal conjugate vaccine serotypes will be summarised descriptively at 18 weeks and 12 months of age. Groups 1 vs 2, 3 v 4 will be compared using similar methods to those for GBS IgG concentrations.

- Infant exploratory endpoint 2: Proportions of infant participants with GBS colonisation assessed by nasal/rectal swabs at birth and at 6 weeks and 18 weeks of age will be calculated with exact binomial 95% confidence intervals for each group. Comparison between groups (GBS v Placebo within each HIV strata) will be by Fisher's exact test.

- Infant exploratory endpoint 3: For each serotype, GMCs will be calculated from dried blood spots in infant participants at births for each group with 95% confidence intervals.

A placebo controlled clinical trial investigating the safety and immunogenicity of GBS6 in pregnant women with and without human immunodeficiency virus (HIV) infection and their infants

Protocol Version 5.0, Dated 01/02/2023

Protocol Version/date 5.0,01/02/2023
R&D Protocol Code Number:
Page:38

Note that detailed analyses of all the endpoints including additional exploratory analyses and graphical displays will be described in the SAP.

A placebo controlled clinical trial investigating the safety and immunogenicity of GBS6 in pregnant women with and without human immunodeficiency virus (HIV) infection and their infants

Protocol Version 5.0, Dated 01/02/2023

Protocol Version/date 5.0,01/02/2023
R&D Protocol Code Number:
Page:39

7. Trial design

This is a randomised, placebo controlled, double-blind, parallel group study which will be based at Kawempe Specialised National Referral Hospital, Kawaala and Komamboga Health Centre III and Wakiso and Kisenyi Health Centre IV, Uganda.

Subjects will be a randomized 1:1 to GBS6/placebo stratified by baseline HIV status:

1. HIV-uninfected women, placebo (saline) in pregnancy;
2. HIV-uninfected women, GBS6 in pregnancy;
3. HIV-infected women, placebo (saline) in pregnancy;
4. HIV-infected women, GBS6 in pregnancy;

	HIV-uninfected pregnant woman	HIV-infected pregnant woman

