9.2. Data collection

Data will be collected regarding: previous vaccinations (mother), parity, gravida, illnesses or complications of pregnancy, gestation at birth, birth weight, HIV status (mother and infant), syphilis and hepatitis B and hepatitis C status, CBC, renal and liver function, CD4 count, HIV viral load, medications, maternal age, ethnicity, infant sex and number of siblings. All patient information will be directly inputted into the database using only the unique study identifier.

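### The only safety power statement is for prematurity, but no endpoint or planned analysis names preterm birth, and the stated 80% needs a pooled comparison that the plan does not make

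*Protocol*

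**What the plan says.** Protocol 6.1 states that the analyses are largely descriptive and that the sample size reflects what the site can achieve. It then gives one power statement for safety, with prematurity as an example of a common pregnancy outcome: 300 women in total give 80% power at the 5% level "to detect an increase in prematurity outcomes from a background rate of 10% in the placebo arm", when the rate on GBS6 is 22% or higher.

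Protocol 5.2 lists six primary safety endpoints, four maternal and two infant. The closest maternal one is endpoint 4: "Occurrence of SAEs, MAEs, and obstetric complications (peripartum, intrapartum, and postpartum) throughout the study". The term obstetric complications is not defined further. Infant primary endpoint 2 covers, besides serious and medically attended events, "AEs of special interest (major congenital anomalies, developmental delay, and suspected or confirmed GBS infection"; section 14.11 repeats the same three items. Neither the primary nor the secondary and exploratory endpoints mention preterm birth, prematurity or gestation at delivery.

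Protocol 6.3 gives each primary endpoint proportions with exact binomial intervals by group, and Fisher's exact test of GBS6 against placebo within each HIV stratum. On design, section 7 says: "Subjects will be a randomized 1:1 to GBS6/placebo stratified by baseline HIV status", with 75 women in each of four groups.

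The raw material for a preterm analysis exists. Section 9.2 collects "gestation at birth, birth weight"; 9.6 includes a dating ultrasound at screening; 11.1.5 records pregnancy outcome at delivery; and 8.3 (item 11) defines premature delivery as before 37 0/7 weeks.

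**The concern.** The protocol states what it can detect for one safety outcome, and then specifies no analysis of that outcome. Dosing is at 27 0/7 to 35 6/7 weeks, so every dosed woman is still at risk of delivering before 37 weeks, and preterm birth is the pregnancy outcome that 6.1 itself singles out. If the plan is followed as written, no defined result corresponds to the 10% v 22% statement.

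There is a second mismatch. The statement refers to all 300 women, that is 150 per arm, but the primary comparisons are made separately in HIV-uninfected and HIV-infected women. A reader who takes 80% as the trial's sensitivity to a doubling of preterm birth would be relying on a comparison that is not planned. A null result would then look more reassuring than it is.

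**Working it through.** **Where preterm birth could appear.**

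- Maternal endpoints 1 and 2: solicited reactions within 7 days. Not applicable.
- Maternal endpoint 3: adverse events to 1 month. It could include preterm labour in that window; not named.
- Maternal endpoint 4: serious events, medically attended events and obstetric complications to 12 months post-delivery. It could include it; not named.
- Infant endpoint 1: unsolicited events from birth to 6 weeks. It could include it; not named.
- Infant endpoint 2: serious events, events of special interest and medically attended events to 12 months. Prematurity is not on the special-interest list.
- Secondary and exploratory endpoints: antibody levels, placental transfer, colonisation, breast milk and responses to routine infant vaccines. Not applicable.
- Pregnancy outcomes listed as SAEs in 14.5.3 and 14.8: preterm birth is not among them.
- Section 8.7(g): premature labour or rupture of membranes within 14 days, counted in GBS6 recipients only. This is a stopping rule, not a comparison.
- Section 14.13: hospitalisation before 37 weeks is AE-related. This brings in most facility births before 37 weeks, but also any other admission before 37 weeks, so it does not give a preterm-birth rate.

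**Reproducing the stated power.** Inputs from 6.1: p1 = 0.10, p2 = 0.22, alpha 5%, power 80%, N = 300, hence 150 per arm under 1:1 allocation. Sidedness and dropout are not stated; I assume two-sided and none. The mean proportion is 0.16.

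n per arm = [1.960 × √(2 × 0.16 × 0.84) + 0.842 × √(0.10 × 0.90 + 0.22 × 0.78)]² / 0.12²
= [1.016 + 0.430]² / 0.0144 ≈ 146, or 292 in total.

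Power at n per arm = Φ{[0.12 × √n − 1.016] / 0.5115}.

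- n = 150: Φ{(1.470 − 1.016) / 0.5115} = Φ(0.887) = 81%.
- n = 75: Φ{(1.039 − 1.016) / 0.5115} = Φ(0.045) = 52%.

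The 80% is therefore reproduced for the pooled comparison. Enumerating Fisher's exact test, the test named in 6.3, gives 77.5% at 150 v 150 and 43.7% at 75 v 75. With 75 per group, the vaccine-arm rate detectable with 80% power against 10% is about 28% (normal approximation) or 29% (Fisher), not 22%.

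Other conventions: a continuity correction would need 162 per arm. A one-sided 5% test would need 115 per arm, with power 89% at 150 v 150 and 64% at 75 v 75. None of these brings the within-stratum comparison to 80%.

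**Illustration of reading prematurity through a composite.** Suppose that endpoint 4 is analysed as one proportion, and that other qualifying events occur in a fraction q of women in both arms, independently of prematurity. The composite rate is 1 − (1 − q)(1 − p).

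- q = 0.2: 28.0% v 37.6%; power 43% at 150 v 150 and 24% at 75 v 75.
- q = 0.6: 64.0% v 68.8%; power 14% and 9%.

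The protocol gives no value for q. These figures show the direction of the effect, not an estimate of it.

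**The case against.** The strongest reply is that 6.1 does not rest the size on prematurity. It rests it on feasibility, calls the analyses largely descriptive and gives prematurity as an example. That stands: a reader might infer that the trial was sized on preterm birth, and the text does not support this. Prematurity is nevertheless the only safety outcome given a power figure.

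Second, preterm birth is not ignored. The opening of section 14 says that pregnancy outcome is collected and analysed. Section 14.13 treats hospitalisation before 37 weeks as AE-related, 14.8 makes inpatient hospitalisation an SAE criterion, and 8.1 requires willingness to deliver at the study facilities. A reader might infer that an uncomplicated birth at 36 weeks could go unrecorded for both mother and infant; these passages make that unlikely for a facility birth, and I do not claim it. What remains is that being counted somewhere among serious events is not a preterm-birth rate.

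Third, the end of 6.3 leaves detailed and additional exploratory analyses to the SAP, which may list complications by type. That is a fair expectation for tables. The endpoint list and the form of the comparison are fixed in the protocol, though, and there they disagree with 6.1.

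Fourth, a reader might take the composite figures as showing that most of an effect would be hidden. They depend on assumed rates and independence, and on endpoint 4 being a single proportion. Section 6.3 speaks of proportions in the plural for that endpoint, which fits separate reporting by category. Even then, preterm birth would sit inside an undefined obstetric category.

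**Conclusion.** The point holds as an internal mismatch between 6.1 and 5.2/6.3, not as an error of arithmetic. The protocol attaches 80% power to an outcome that is neither an endpoint nor the subject of a planned between-arm comparison. The figure is right for a pooled 150 v 150 comparison (81% by normal approximation, 78% by Fisher). For the within-stratum comparisons used for every primary endpoint, it falls to about 52% or 44%. These numbers assume two-sided 5% testing, the 10% and 22% rates in 6.1 applying in both HIV strata, and no dropout. The conclusion that preterm birth lacks a named analysis needs none of these assumptions. It is worth correcting because the remedy is cheap, and because the sentence in 6.1 would otherwise support a reassurance that the planned analysis cannot give.

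**What to change.** In the synopsis, 5.2 and 6.3, name birth before 37 0/7 weeks (the definition already in 8.3) as a separately reported safety outcome, for example as a listed component of maternal primary endpoint 4. Take gestation from the study dating ultrasound, and use all dosed women as the denominator, because the infant safety population in 6.2 contains only enrolled infants. Report it in each of the four groups with exact 95% confidence intervals, and add a GBS6 v placebo comparison pooled over HIV status and stratified by it, so that the analysis matches the 300 women in 6.1. Reporting by group alone would leave the power statement unmet.

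The alternative is to remove the sentence from 6.1, or restate it for the analysis actually planned: with 75 per group and Fisher's test, 80% power needs a vaccine-arm rate of about 29% against 10%.

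The first option costs a wording change, a table row and one more safety comparison. It needs no new data, since gestation at birth and pregnancy outcome are already recorded.

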6.2 Study populations

Safety population

A safety population will be defined separately for, maternal participants and their infant participants. For the safety analyses, maternal participants will be analysed according to the investigational product received and infant participants will be analysed according to the investigational product their mothers (maternal participants) received.

- Maternal participants: All maternal participants receiving a dose of GBS6 or placebo will be included in the safety population.
- Infant participants: All infant participants who are enrolled in the study will be included in the safety population.

Immunogenicity population

Two populations will be defined separately for maternal participants and their infant participants: evaluable immunogenicity population and modified intent-to-treat (mITT) populations. Immunogenicity data will be analysed separately for maternal participants and their infant participants.

For the immunogenicity analyses, maternal participants will be analysed according to the investigational product received for the evaluable immunogenicity population and the investigational product as randomised for the mITT population. Infant participants will be analysed according to the investigational product received by their mothers (maternal participants) for the evaluable immunogenicity population and the investigational product assigned to

A placebo controlled clinical trial investigating the safety and immunogenicity of GBS6 in pregnant women with and without human immunodeficiency virus (HIV) infection and their infants

Protocol Version 5.0, Dated 01/02/2023

Protocol Version/date 5.0,01/02/2023
R&D Protocol Code Number:
Page:32

their mothers (maternal participants) for the mITT population. The evaluable immunogenicity population is considered to be the primary population for the immunogenicity analyses.

- Maternal participants

To be included in the evaluable immunogenicity population, the maternal participant must have been eligible for the study, have received GBS6 or placebo as randomised, have had blood drawn within the specified time frames, have at least one valid and determinate assay result for the proposed analysis, and have no other major protocol violations. To be included in the mITT population, the maternal participant must be randomised and have at least one valid and determinate assay result related to the proposed analysis.

- Infant participants

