6.3 Statistical methods

Safety data will be analysed separately for maternal participants and their infant participants.

- Descriptive analysis

A flowchart will be used to summarise the number of mothers approached, consented, recruited, assigned to the different study arms, receiving the intended vaccines, completing the study protocol and analysed for the primary outcome, as recommended by the CONSORT statement (<http://www.consort-statement.org/>).

- Statistical significance and confidence intervals

A placebo controlled clinical trial investigating the safety and immunogenicity of GBS6 in pregnant women with and without human immunodeficiency virus (HIV) infection and their infants

Protocol Version 5.0, Dated 01/02/2023

Protocol Version/date 5.0,01/02/2023
R&D Protocol Code Number:
Page:33

MAKERERE UNIVERSITY
SCHOOL OF MEDICINE
APPROVED AMENDMENT
Valid Until

★ 30 NOV 2023 ★

RESEARCH & ETHICS COMMITTEE
[name]

5% significance will be used and 95% confidence intervals.

- Statistical software

Statistical analyses will be performed on STATA version 15 or similar.

- Missing data

Analysis will be by modified intention to treat (mITT), meaning individuals are analysed according to the group they are randomised to, but only those with at least one blood taken and antibody result will be included, with missing data (e.g. from withdrawals, non-compliers) assumed missing at random. Missing data will be excluded from relevant analyses. The mITT analysis will include blood samples taken outside the recommended timing. A per-protocol analysis will also be performed if there are major protocol deviations. Spurious data will be checked to source records and investigated but included if no cause is identified.

- Outliers, censored data and non-normal data

Outliers will be included in the analyses and investigated assuming no errors have occurred. We will assign all results of <2 a value of 1 for calculation of geometric means. Antibody concentrations will be log-transformed for analyses of mean antibody levels.

- Statistical analysis for each objective and outcome

Statistical Analysis of primary endpoints

The followings are the primary analyses for each of the outcomes related to primary objectives.

- Maternal primary endpoint 1:

Proportion of maternal participants reporting solicited local reactions within 7 days following administration of GBS6 vaccine will be calculated with exact binomial 95% confidence

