Proportions of infants with SAEs, AEs of special interest (major congenital anomalies, developmental delay, and suspected or confirmed GBS infection), and MAEs through 12 months of age and any unsolicited events leading to study withdrawal following administration of GBS6 vaccine will be calculated with exact binomial 95% confidence intervals for each group. Comparison between groups (GBS v Placebo within each HIV strata) will be by Fisher's exact test.

Statistical analysis of secondary endpoints

The followings are the primary analyses for each of the outcomes related to secondary objectives.

- Maternal secondary endpoint 1:

Antibody levels for GBS serotype-specific antibody concentrations measured at baseline, 2 weeks, 1 month after vaccination, at delivery, and 6 weeks after delivery in HIV positive and HIV negative women will be described using box-and-whisker plots with a log-scale y-axis. GMTs of GBS serotype specific antibody concentrations measured at baseline, 2 weeks, 1 month after vaccination, at delivery, and 6 weeks after delivery in HIV positive and HIV negative women will be calculated with 95% confidence intervals post vaccinations and the groups will be compared using unpaired t-tests or the Kruskal Wallis test if log-titres are not normally distributed.

Reverse cumulative distribution curves (RCDCs) of antibody concentrations by vaccine groups will be generated for each GBS6 serotype. Additionally, graphs of geometric means and the associated 95% CIs of the antibody concentrations will be presented at each analysis time point by vaccine group and serotype. The proportions of participants achieving defined GBS6 serotype specific IgG concentrations will be summarised descriptively at prespecified time points as counts and percentages with 2-sided 95% exact CIs by vaccine group and HIV

A placebo controlled clinical trial investigating the safety and immunogenicity of GBS6 in pregnant women with and without human immunodeficiency virus (HIV) infection and their infants

Protocol Version 5.0, Dated 01/02/2023

Protocol Version/date 5.0,01/02/2023
R&D Protocol Code Number:
Page:36

MAKERERE UNIVERSITY
SCHOOL OF MEDICINE
APPROVED AMENDMENT
Valid Until

★ 30 NOV 2023 ★

RESEARCH & ETHICS COMMITTEE
[name]

status. Groups 1 vs 2, 3 v 4 will be compared by a t-test or Kuskal-Wallis test if logged data are not normally distributed.

- Maternal secondary endpoint 2:

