11.4. Participant withdrawal

An investigator and/or sponsor can withdraw a participant from the study if deemed appropriate. In addition, if a participant fails to continue to meet the inclusion criteria, new

A placebo controlled clinical trial investigating the safety and immunogenicity of GBS6 in pregnant women with and without human immunodeficiency virus (HIV) infection and their infants

Protocol Version 5.0, Dated 01/02/2023

Protocol Version/date 5.0,01/02/2023
R&D Protocol Code Number:
Page:73

information becomes available that would exclude the participant, or the participant develops a condition or situation that would meet exclusion criteria, the participant may be considered for withdrawal. Infant participants born from vaccinated maternal participants may be considered for withdrawal from study procedures for any medical condition(s) that, in the opinion of the investigator, would contraindicate blood sampling.

Reasons why a participant may discontinue or be withdrawn from the study include, but are not limited to, failure to meet entrance criteria (screening failure), AE, death, protocol violation, lost to follow-up, no longer willing to participate in the study, study terminated by sponsor, investigator declined further study participation, or any other reason. Participants who have received the investigational product will not be replaced regardless of the reason for withdrawal.

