30 NOV 2023

RESEARCH & ETHICS COMMITTEE
[name]

Abbreviations: EDD = estimated date of delivery; paper diary card = electronic diary; GBS = group B streptococcus; HBV = hepatitis B virus; HCV = hepatitis C virus; HIV = human immunodeficiency virus; LMP = last menstrual period; Postdeliv. = postdelivery; Vacc. = vaccination; CBC – complete blood count.

- a. Visits at 2 weeks and 1 month after vaccination will not be performed if delivery occurs before the visits. Once delivery occurs, the visit windows are calculated based on delivery date.
- b. Vital signs include weight, height (only required at Visit 0), oral temperature, sitting blood pressure and pulse rate, and respiratory rate.
- c. If abnormal laboratory tests are reported at Visit 0 and the investigator believes the results to be erroneous, the abnormal laboratory parameters may be retested.
- d. All blood volumes are approximate.
- e. Sample may be collected up to 72 hours after delivery.
- f. Participants will provide (in a paper diary card) a baseline assessment of prompted systemic events prior to vaccination and participants will record (in a paper diary card) reactogenicity events each evening for 7 days following vaccination. Remind participants that study staff may contact them to obtain additional information on Grade 3 events entered into the paper diary card. Ask participants to contact the investigator or site staff immediately if they are prompted by the paper diary card from Day 1 to Day 7 following vaccination to determine if an unscheduled visit is required.
- g. Prior to vaccination, 2 swabs will be collected during the clinic visit from the following sites: 1 rectal and 1 vaginal.
- h. Rectal/vaginal swabs may be collected from onset of labour up to 72 hours after delivery.
- i. Any participant found to be pregnant during the study will be followed up to outcome of the pregnancy.

A placebo controlled clinical trial investigating the safety and immunogenicity of GBS6 in pregnant women with and without human immunodeficiency virus (HIV) infection and their infants

Protocol Version 5.0, Dated 01/02/2023

Protocol Version/date 5.0,01/02/2023
R&D Protocol Code Number:
Page:82

Schedule of Activities for Infant Participants						
Visit Number	1	2	3	4	5	6
Equivalent Visit Number for Maternal Participants	4	5	6	7	8	9

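### Section 6.1 quotes immunogenicity power for 75 analysed women per group, but 75 is the number enrolled, and the figure leaves no room for any loss

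*Protocol*

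**What the plan says.** Section 6.1 plans that "approximately 300 pregnant women will be enrolled in this study", 75 in each of the four vaccine-by-HIV cells. It then says that "the standard deviation (SD) of the GMT responses to serotypes Ia, Ib and III is expected to be around 2.55 log e units" and concludes: "With 75 women per group, the study will have at least 80% power (5% alpha) to detect at least 3.24-fold higher antibody responses". No allowance for withdrawal, missing samples or non-evaluable results is stated. The same section says that the analyses are largely descriptive and that the size reflects what the site can achieve.

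Section 6.2 fixes who is analysed: "The evaluable immunogenicity population is considered to be the primary population for the immunogenicity analyses". To be in that set a woman must have been eligible, have received the product as randomised, have had blood drawn in the specified window, have a valid assay result and have no other major violation. Section 6.3 leaves missing data out of the relevant analyses. It plans t-tests of Group 1 v 2 and Group 3 v 4, so each test compares at most 75 with 75.

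Section 11.4 adds: "Participants who have received the investigational product will not be replaced regardless of the reason for withdrawal". Footnote a to Table 1 (the maternal schedule in Section 11.5) adds: "Visits at 2 weeks and 1 month after vaccination will not be performed if delivery occurs before the visits".

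**The concern.** A power figure describes the number of results that enter the test. Section 6.1 puts the enrolment target in that place, while other sections reduce the analysed number below it and give no way to make up losses after vaccination. If the figure has no slack at 75, a claim of at least 80% power fails as soon as anyone is lost.

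What is at stake is how a null or imprecise GBS6 v placebo comparison within an HIV stratum is read. Section 19 presents the trial as well powered for immunogenicity, so a reader would take 80% as a floor for the analysed data. The safety analyses and the conduct of the trial are not affected.

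**Working it through.** **Inputs.** SD 2.55 log-e units, ratio 3.24, 75 per group, 80% power and 5% alpha (Section 6.1); t-test on log values within HIV stratum (Section 6.3). Section 6.3 says "5% significance will be used and 95% confidence intervals" without naming sidedness for the test. I assume two-sided, in line with its "2-sided 95% exact CIs by vaccine group and HIV" status.

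**Formula.** With n analysed per group, δ = ln(3.24) = 1.1756, standard error = 2.55 × √(2/n), noncentrality = δ / standard error, and df = 2n − 2. Power is the probability that a noncentral t with these parameters exceeds the two-sided 5% critical value in absolute size.

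**Reproducing the plan's figure (n = 75).** Standard error = 2.55 × √(2/75) = 0.4164. Noncentrality = 1.1756 / 0.4164 = 2.823. With df = 148 the critical value is 1.976. Power = 80.09%. The ratio with exactly 80% power is 3.236, which rounds to the stated 3.24. A one-sided test (88.1%) or pooling the strata at 150 v 150 (97.8%) does not give 80%. The stated figure is therefore the within-stratum two-sided calculation with all 75 analysed.

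**Slack.** At n = 74: standard error 0.4192, noncentrality 2.804, power 79.55%. Under the t-test that the protocol plans there is no slack. The cruder normal approximation gives 80.6% at 75, 80.07% at 74 and 79.5% at 73, so even that leaves room for only one loss per group.

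**Size under assumed losses.** The protocol gives no loss rate, so 5%, 10% and 20% are assumptions. Evaluable n is 75 × (1 − loss), rounded down.

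| Assumed loss | n per group | Noncentrality | Power at 3.24-fold | Ratio detectable at 80% |
|---|---|---|---|---|
| 0% | 75 | 2.823 | 80.1% | 3.24 |
| 5% | 71 | 2.747 | 77.9% | 3.34 |
| 10% | 67 | 2.668 | 75.5% | 3.47 |
| 20% | 60 | 2.525 | 70.7% | 3.72 |

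**Where losses arise.** Some apply at every time point: exclusion from the evaluable set, missing or invalid results, and withdrawal after vaccination. One applies only to the 2-week and 1-month bloods. Vaccination is allowed up to 35 6/7 weeks and the 1-month visit falls 28 to 42 days later, so for the latest-vaccinated women it is due at 39 6/7 to 41 6/7 weeks. Some of them will have delivered by then.

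**The case against.** The strongest reply is that the sentence is conditional on 75 women per group and is correct under that condition. That stands: a reader might infer a calculation error, and there is none. The fault is that the condition is the enrolment target rather than the number expected in the analysis.

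A reader might also infer that the protocol's rules make 75 evaluable women per group impossible. They do not. No loss rate is given, women who withdraw before vaccination may be replaced (Section 10.11), and Section 8 allows no eligibility waivers. The rules make full evaluability unlikely, no more.

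On the analysis set, the missing-data text in Section 6.3 says that analysis will be by mITT and will keep samples taken outside the recommended timing, whereas Section 6.2 makes the evaluable set primary. That conflict needs settling. Under mITT fewer women would be lost, but an absent result is still dropped, and one absent result per group is enough.

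The skipped visits should not be pressed too far. When delivery comes first, the delivery visit is held instead and an immunogenicity blood is taken up to 72 hours after delivery, so these women still give a post-vaccination result. Delivery is itself a time point of maternal secondary endpoint 1. A reader might treat everyone who has delivered by day 42 as lost at 1 month. The documents do not support that: the window opens at day 28, so many of those women could already have been bled, and the share depends heavily on gestation at vaccination, whose distribution the protocol does not give. As an illustration, I assumed normally distributed delivery with mean 39.0 to 39.6 weeks and SD 1.4 to 2.0. If vaccination is spread evenly over the whole permitted window, about 9 to 15% have delivered before day 28; if it is spread over 27 to 32 weeks, about 0 to 1%.

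Finally, the SD is itself approximate. At an SD of 2.4, 67 per group would still give 80.4% power; at 2.7, 75 per group would give only 75.5%. That uncertainty runs both ways and does not supply a reserve.

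**Conclusion.** The concern holds in a limited form. The 80% is right for 75 analysed per group and is stated for 75 enrolled, with no loss allowed for. Under the planned t-test it falls below 80% with one loss per group (79.6%). For assumed losses of 5 to 20%, power for a 3.24-fold difference is about 78% down to 71%, and the detectable ratio rises to between 3.34 and 3.72. These figures are per serotype and rest on the protocol's SD of 2.55, a two-sided 5% test and equal losses in both groups.

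The 1-month time point will have some further loss through earlier delivery. Its size cannot be fixed from the documents. Severity is minor: immunogenicity is a secondary objective, the analyses are largely descriptive, and the size was chosen for feasibility.

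**What to change.** Rewrite the power statement in Section 6.1 for evaluable women, name the assumed loss, and say that 75 is before losses. For example: 75 women per group will be enrolled; with an assumed 5%, 10% or 20% non-evaluable (71, 67 or 60 per group), power per serotype for a 3.24-fold difference is about 78%, 75% or 71%, and the ratio detectable at 80% power is about 3.34, 3.47 or 3.72 (SD 2.55 log-e units, two-sided 5%). Add a sentence saying that the 1-month time point will lose further women through earlier delivery, to an extent that depends on gestation at vaccination. While editing, make Sections 6.2 and 6.3 agree on which immunogenicity population is primary, since the evaluable number depends on it.

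The cost is a few sentences and a slightly less favourable stated figure. It needs no extra participants and no change to visits, endpoints or tests.
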